Protocol Synopsis for Research Project Involving Human Subjects

PROTOCOL INFORMATION

Title of Research Activity: The Health and Aging Brain Study: Health Disparities TAU PROJECT

Name of Principal Investigator: *[name]*

Names of each Co-Investigators: *[name] (Co-PI), PhD.*

[name], DO (Co-I and study doctor)

Sponsoring Agency / Company (if applicable): *National Institute of Aging*

Sponsor's Protocol Number (if applicable): *R56AG058533*

A. Specific Aims –

Despite a primary goal of the National Alzheimer's Project Act (NAPA)¹ being to "improve outcomes for ethnic and racial minority populations that are at higher risk for Alzheimer's disease(AD)", very little research has been conducted among the U.S. Hispanic population^{2,3}. By the year 2050, the percentage of Hispanics in America age 65 and above will nearly triple, while declining or remaining flat among other ethnic groups⁴. With 65% of the U.S. Hispanic population being Mexican American⁵, this ethnic group reflects a rapidly growing segment of the aging population that is at increased risk for MCI and AD^{6,7} at younger ages^{2,8,9}. Additionally, Hispanic/Latinos will experience the largest growth in AD and AD related dementias (ADRDs) between now and 2060¹⁰. With the generation of the 2018 AT/N Framework¹¹, there is an increased focus on amyloid (A), tau (T) and neurodegenerative (N) markers to understand AD as a biological construct. However, as pointed out in the framework, there is a need to understand these biological markers among diverse and community-based populations. Despite the tremendous focus on amyloid, tau and neurodegenerative markers, no prior work has examined PET tau burden among Mexican Americans despite the fact that tau burden has been found to fluctuate as a function of race/ethnicity at autopsy and CSF studies¹²⁻¹⁵. Here we propose to conduct the first-ever pilot study of tau burden among Mexican Americans.

There is now a tremendous push to move tau PET tracers to Regulatory approval in order to advance novel intervention trials and to guide clinical care. Flortaucipir(¹⁸F), laboratory name **¹⁸F-AV-1451**, is the single most investigated PET tracer for the study of cerebral tau burden. In fact, a PubMed search (7/23/19) using the search term "AV1451" identified n>100 publications; however, when the term "Hispanic" was added, no results were identified. With novel clinical trials (intervention and prevention)

targeting both amyloid and tau, there is a huge need to understand tau burden among Mexican Americans. Prior work by our team, and others, has shown that when compared to non-Hispanic whites, Mexican Americans (1) are at increased risk for MCI and AD⁶, (2) are diagnosed at a more advanced stages of disease progression^{3,8} (3) develop MCI and AD at younger ages^{2,8,12}, (4) have a lower frequency of the ApoE ϵ 4 allele^{2,3,16}, (5) suffer from a disproportionate burden of modifiable risk factors for MCI and AD (e.g. diabetes, depression)^{2,3,17} and (6) demonstrate an AD proteomic profile that is metabolic in nature¹⁸. In our HABLE-Amyloid pilot project, we now have data showing that amyloid burden among Mexican Americans that have been clinically diagnosed as MCI or AD (1) have significantly lower amyloid burden as compared to non-Hispanic whites; however, they also (2) have comparable levels of neurodegeneration as measured by plasma NfL levels. Therefore, our data demonstrates medical, genetic, proteomic and amyloid differences among Mexican Americans diagnosed with MCI and AD as compared to non-Hispanic whites. In fact, we have identified cognitive loss at younger ages that is associated with neurodegeneration in the absence of amyloid among Mexican Americans. Given that tau is associated with global neurodegeneration, it is possible that Mexican Americans are suffering altered levels of tau burden when compared to non-Hispanic whites. This also suggests that the “accepted” sequence of pathological burden could be fundamentally different among this population. However to date no studies are examining Tau burden via PET scan in Mexican Americans. Moreover, questions remain regarding the feasibility of recruiting this population into Tau research studies.

This study seeks to address this gap through the achievement of the following specific aims: 1) Conduct a pilot study regarding the feasibility of recruiting Mexican Americans with known amyloid status into a PET tau scan study, 2) Examine the prevalence of tau burden among community-dwelling Mexican Americans suffering with known amyloid burden.

The current study is **highly significant** for several reasons: (1) this is the first-ever study of the tau hypothesis among Mexican Americans; (2) this study will examine how tau is potentially differentially present among Mexican Americans; (3) this study will demonstrate, for the first time, the feasibility of recruiting Mexican Americans into a PET tau scan study.

B. Background and Significance -

The long-term goal of this research is the generation and validation of biomarkers of Alzheimer’s disease (AD) among Mexican Americans. Despite the rapidly growing Mexican American elderly population, little research has been conducted on AD among this ethnic minority group. Research that has been conducted suggests that a significant health disparity exists with Mexican Americans (1) being at increased risk for AD, (2) being diagnosed with AD at younger ages and more advanced stages, (3) experiencing significantly longer disease duration as well as delays in diagnosis and treatment, and (4) being misdiagnosed due to invalid/inaccurate measures. The 2018 AT/N Framework has now provided a biologically-based system for examining the emergence and progression of AD; however, all of the data in support of this framework is based on non-Hispanic whites. This means that our fundamental understanding of the pathological processes underlying AD is not reflective of our diverse U.S. population. Additionally, the research underlying our conceptualization is based on clinic-based samples, which are substantially biased. Therefore, here we will conduct a pilot study of cerebral tau burden among Mexican Americans with known amyloid status to set the stage for a large-scale community-based study of the 2018 AT/N Framework among a diverse cohort.

A tremendous amount of progress in neuroimaging biomarkers of AD has been accomplished within the last decade, which is largely due to the Alzheimer’s Disease Neuroimaging Initiative (ADNI), the most

comprehensive study of AD globally to date. In fact the FDA has now approved multiple PET imaging biomarkers of amyloid for use in the diagnostic process. Flortaucipir(18F) is the single most studied radiotracer specifically for the detection of brain tau among living patients. Prior to this technology, confirmation of tau pathology was only possible with lumbar punctures or at autopsy. However, in our prior discussions with the HABLE cohort, no participants said they would undergo lumbar punctures. Additionally, no prior work has been undertaken to determine if neuroimaging biomarkers of tau and amyloid AD vary according to ethnicity or if ethnicity impacts the appropriate diagnostic cut-values.

C. Preliminary Studies

Our group has extensive experience recruiting Mexican Americans into aging research and are leaders in the field of aging, MCI and AD among this ethnic minority group. The team has recruited n>2000 Hispanics (primarily Mexican Americans) into multiple projects, including the Health & Aging Brain among Latino Elders (HABLE) recruitment protocol of the Health & Aging Brain Study, the Texas Alzheimer's Research & Care Consortium (TARCC), Project FRONTIER and the CMS-funded MIGHTY Care waiver project. Together these efforts have resulted in over 50 peer-reviewed publications with over 20 emphasizing underserved populations (see PIs CV).

Our current team currently runs one of the most comprehensive studies of Mexican American brain aging ever conducted, the Health & Aging Brain Study HD: Health Disparities (2016-128). The goal of the HABLE HD parent study is to examine health disparities in aging. This project will recruit 1000 MA and 1000 non Hispanic whites for baseline and 24 month follow up.

In 2018, we were funded to obtain PET scans on a subset of the cohort. The PET scans were separated into 2 IRB protocols (Amyloid project 2017-165 and the TAU Project). The TAU Project will leverage the ongoing Health and Aging Brain Study: Health Disparities Amyloid Project (IRB# 2017-165) project to conduct tau PET scans among n=40 Mexican Americans.

D. Investigator Experience

The PI, and his research team, has extensive experience building and maintaining community-based as well as clinic-based longitudinal research cohorts. Our team has recruited n>8,000 participants from underserved communities into funded programs from the DFW region since 2012. CV attached.

E. Experimental Design and Methods

1) Methods and Procedures -

Overview

The Health and Aging Brain Study HD: Amyloid Project (2017-165) is currently recruiting up to 1000 participants from the Health and Aging Brain Study HD: Health Disparities (2016-128) to undergo amyloid PET scans. All other research components are captured as part of the parent IRB protocol. Here, we propose to re-contact n=40 participants who self-identify as Mexican American, that have already undergone amyloid PET scans as part of IRB 2017-165, and have given permission for re-contact.

Participants will be re-contacted using the **Recruitment Script (see attachment)**. Please note that the script for this study is minimal. Our team has extensive experience recruiting older underserved individuals

into research. We have found our participants prefer to have discussions face to face rather than over the phone. Additionally, during the amyloid study, we informed participants of the potential for another PET scan study in the future.

For those individuals who wish to participate, an appointment will be set up for him/her to come to our research offices for an in-person visit to conduct the consent and screening visit. This can take place in one visit or spread out over multiple visits. The study doctor will review the information collected in the medical exam and determine eligibility.

If the participant meets eligibility criteria, the research team will schedule an appointment for the participant to receive the brain scan at an imaging center. Participants will undergo a PET scan. Participants will be screened by the research team during the medical exam, and by the imaging center staff before they are scanned. The imaging center personnel will carry out their standard/internal procedures for verifying PET scan eligibility. If the imaging center identifies a safety concern they will notify the research team.

Participants unable to undergo a scan will be withdrawn from the study by the research team. The participants may meet a member of the research team at the imaging facility on the day of the scan.

Participants must complete the PET scan in order to be compensated for his/her time.

The data collected in this study will be linked with the participant's data collected in The Health and Aging Brain Study HD: Health Disparities IRB# 2016-128 and The Health and Aging Brain Study: Health Disparities Amyloid Project IRB# 2017-165.

This study will be posted on clinicaltrials.gov. This study will cross reference AVID's IND and an IND has been obtained for the UNTHSC site, FDA IND Number 145437 Any SAEs will be reported to the FDA, AVID, and the IRB.

The following may take place over multiple visits based on the participant's schedule and scanner availability.

Consent

All participants will sign an informed consent before they are enrolled. A copy of the consent document can be found in the **Attachments**. The consent form covers all possible parts of the study, and explains the risks and benefits of participation. Individuals who are unable to read and understand the written consent will be provided with an oral presentation of the consent form, and then their signature will be obtained. This process must be observed and attested to on the consent form by a witness. For individuals with Alzheimer's disease who are unable to provide independent consent, informed consent will be obtained from caregivers and consent from the participant will be obtained. Consent forms will be available in English and Spanish. Spanish speaking only participants will be consented by bi-lingual research staff. **[Note: Spanish versions will be submitted once IRB approval is received].**

Screening

After consenting, participants will be asked to complete a medical exam to determine eligibility. During this

visit, medical personnel will obtain the participant's medical history, blood pressure, collect a list of medications, and conduct an ECG. The participants will undergo a fasting blood draw for standard clinical labs. For female participants who experienced a period in the last 2 years, a urine pregnancy test will be performed. The medical exam will be conducted by the study nurse practitioner and the information obtained during this screening visit will be used by study doctor to determine participant eligibility. Below is a detailed outline of screening procedures. Please note if at any time during the screening visit it is determined the participant is ineligible, the visit will be discontinued. However, a person may not complete the scan until all procedures are completed and the study doctor has deemed the subject meets criteria for inclusion. The medical exam will be conducted by a licensed Nurse Practitioner ([name]) or the study doctor ([name]). Final judgement regarding eligibility will be made by the study doctor ([name]).

Screening procedures

1. Medical History and medication review
2. Urine Pregnancy test (if necessary for female participant's)

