3. ECG
The NP/doctor will conduct the ECG. Clinically significant findings on ECG specifically Bazett's¹⁹ corrected QT (QTcB) interval exceeding accepted values (458 msec in males, 474 msec in females) will result in exclusion from the study.
4. Blood work
Participants will be asked to undergo a fasting blood draw. Blood draws will be obtained via venipuncture and up to 20ml will be obtained for this study. Standard clinical labs will be conducted in CLIA certified laboratories and will include comprehensive metabolic panel (CMP), complete blood count with differential (CBC), thyroid panel with TSH and T4, Lipid panel, and HbA1c. Blood samples will be labeled with the participants medical ID and will not be retained for biobanking.

The study doctor will review all the information from the medical exam and determine if the participant meets eligibility criteria.

If a participant is deemed ineligible to participate, data collected from the screening visit will not be maintained for research purposes. However, as this is an FDA regulated study, consents and participant files will be maintained as required by law.

**If there are clinically significant findings on the ECG or clinical labs the participants will be notified and instructed to follow up with their personal medical provider.

The screening visit may take 30 minutes -1 hour.

Positron Emission Tomography (PET) scan for utilizing Flortaucipir.

A positron emission tomography (PET) scan is an imaging test that reveals how an individual's tissues and organs are functioning. A small amount of radioactive material, called a radiotracer, is necessary to show this activity. The precise type of radioactive material and its delivery method depend on which organ or tissue is being studied by the PET scan. For the current study the goal is to obtain tau imaging using a PET scan, which is currently the only pre-mortem method for directly analyzing Alzheimer's disease brain pathology.

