F. Human Subjects - Describe the characteristics of the research population:

1) *Description of subjects* is to include the projected sample size, plans for the selection of subjects, and inclusion and exclusion criteria.

This study seeks to obtain PET tau imaging on n=40 Mexican American participants within known amyloid status currently enrolled in the Health and Aging Brain Study: Health Disparities Amyloid Project (2017-165). Bilingual research assistants will be utilized to interact with Spanish speaking only participants. Participants will be recruited directly from the Health & Aging Brain Study: Health Disparities Amyloid Project protocol. Only those who have been consented for re-contact will be recruited for this study. It should be noted that the Inclusion criteria for the parent study is age 50 and older. The majority of participants in the study are 60 and older.

- 2) *Sample Size:* Up to 40 Mexican American participants from the Health & Aging Brain Study: Health Disparities Amyloid Protocol (2017-165) will be enrolled in this imaging study.
- 3) Describe both *Inclusion / Exclusion Criteria.*

Inclusion Criteria

1. Enrolled in the Health and Aging Brain Study: Health Disparities Amyloid Protocol (2017-165)
2. Self-identified as Mexican American
3. Provided consent to re-contact

Exclusion Criteria:

1. Inability to provide informed consent by self or by proxy.
2. Pregnant or breast feeding women*
3. History of risk factors for torsades de pointes
4. Taking medications known to prolong QT interval.**
5. Clinically significant findings on ECG, specifically Bazett's¹⁹ corrected QT (QTcB) interval exceeding accepted values (458 msec in males, 474 msec in females).***
6. Have clinically significant infectious, cardiac, hepatic, renal, pulmonary, metabolic or endocrine disturbances as defined by medical history and clinical lab values.
7. Presence of other conditions or medications deemed to put the subject at risk by the study physician.
8. Participants may not be in this study if they do not meet the safety criteria to undergo imaging procedures.

Note: Participants will be pre-screened by both the research staff and the imaging facility staff before they are scanned.

Additional information for the bulleted exclusion criteria.

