Another risk related to the research is breach of confidentiality, which we will minimize to the extent possible. All files will be stored behind locked doors in locked file cabinets and on password protected computers. Only the PI and the core research team will have access to the master database that contains all research information.

Unknown Risks

Since this tracer is not FDA approved, there may be risks that are unknown. All SAEs will be reported to the FDA, Avid, and the IRB. This study will also be registered on clinicaltrials.gov.

H. Payment/Compensation-This study pays a flat rate for PET scans, which is as follows:

PET Scan with Flortaucipir: \$150

Participants must complete the scan to receive payment. No partial payments will be given.

**The imaging center may refuse to scan a participant if they identify a reason that the person cannot be scanned safely.

Subject Costs –

The participant will not incur any costs related to this study.

J. List of KEY PERSONNEL

[name]

[name] is PI of the Health and Aging Brain Study and will provide project oversight and

management. [name] will participate in all aspects of the study.

[name]

[name] is a Co-PI and will manage the daily operations of the project, as well outreach operations. Additionally, she will conduct data analysis, blood draws, and participant feedback sessions. [name] will participate in all aspects of the study.

[name], DO

[name] will provide medical oversight for the study and be involved in all research activities. [name] may perform some or all elements of the medical exam. [name] will review the information collected during the screening visit and determine participant eligibility.

[name], NP

[name] is a licensed nurse practitioner and will conduct the medical exam during the screening visit. She will conduct the ECGs, urine pregnancy test, medical history, consensus reviews, and other study procedures. [name] has worked on numerous FDA and NIH funded clinical trials and has significant experience conducting ECGs.

She will provide [name] with the results of the medical exams.

[name]

[name] may recruit, complete study protocols and assist with the medical exam. [name] will assist with all regulatory and IRB submissions. She will participate in outreach activities, recruitment and consent of participant, completion of study protocols, blood draws, scheduling, consensus reviews, and enter data into the research database.

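### Does re-contacting 40 people contradict the plan to obtain tau PET scans on 40?

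*Protocol*

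**What the plan says.** The Protocol uses the figure 40 at three stages.

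- **Approached.** Section E.1, Overview: "Here, we propose to re-contact n=40 participants who self-identify as Mexican American". The sentence adds that they have already had an amyloid scan and have permitted re-contact.
- **Enrolled.** Section F.2 (Sample Size) and Section E.2 (Data Analysis and Data Monitoring) both set enrolment at no more than 40.
- **Scanned.** Section C says the project will "conduct tau PET scans among n=40 Mexican Americans", and Section F.1 says "This study seeks to obtain PET tau imaging on n=40 Mexican American participants".

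Between approach and scan the Protocol provides for losses. Section E.1 makes appointments only for people who want to take part, and after consent there is a medical exam judged against the eight exclusion criteria of Section F.3. Section E.1 also says "Participants unable to undergo a scan will be withdrawn from the study by the research team", and Section H says "The imaging center may refuse to scan a participant if they identify a reason that the person cannot be scanned safely".

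No section states an expected yield, a larger contact list or a replacement rule. The first aim in Section A is to "Conduct a pilot study regarding the feasibility of recruiting Mexican Americans with known amyloid status into a PET tau scan study". On people who fail screening, Section E.1 says "If a participant is deemed ineligible to participate, data collected from the screening visit will not be maintained for research purposes", and its next sentence has their consents and participant files kept as the law requires.

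**The concern.** Read literally, one number stands at both the start and the end of a recruitment chain in which people can drop out at every step. If exactly 40 are approached and exactly 40 scanned, nobody may refuse, be excluded or be turned away at the imaging center. The sentence after the re-contact figure refers to the recruitment script, which places re-contact at the invitation, before anyone has agreed.

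The point bears on both aims. Aim 1 concerns the feasibility of recruitment, so its natural denominator is the number approached. Aim 2 rests on the number scanned. A reader could be left unsure whether the study will report some number x scanned out of 40, or up to 40 scanned out of a larger, unstated number. The sentence on discarding screening data raises the further question of whether screen failures could be counted at all.

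**Working it through.** **Inputs.** Contacts 40 (Section E.1, Overview); scans 40 (Sections C and F.1); enrolment ceiling 40 (Sections E.2 and F.2). The Protocol gives no overall yield y from contact to completed scan, so every y below 1 is an assumption. It gives no significance level, power, effect size or precision target either, so there is no sample-size calculation to reproduce.

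**The stated figure.** Scans = contacts × y. With y = 1, 40 × 1.00 = 40, which is the stated number.

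**If 40 were a fixed contact list.** Approaches needed are 40 / y rounded up, and the chance that all 40 are scanned is y^40.

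| Assumed y | Scans from 40 contacts | Approaches for 40 scans | Chance that all 40 are scanned |
|---|---|---|---|
| 98% | 39.2 | 41 | 0.446 |
| 95% | 38 | 43 | 0.129 |
| 90% | 36 | 45 | 0.015 |
| 80% | 32 | 50 | 0.0001 |
| 50% | 20 | 80 | below 0.0001 |

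The arithmetic is sound. Whether it matters depends on whether the Protocol commits itself to 40 scans from 40 contacts.

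**Setting the passages side by side.**

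1. The statement headed Sample Size is a ceiling, repeated in Section E.2. Fewer than 40 enrolled does not breach it.
2. The scan figure in Section F.1 is what the study seeks, and the one in Section C is a one-line description of the project. Falling short of an aim does not contradict it.
3. The Overview sentence does not say that only 40, or at most 40, will be approached. The recruitment rules in Sections F.1 and F.6 require amyloid-project enrolment, Mexican American self-identification and consent to re-contact. They do not close the list at 40. The amyloid project recruits up to 1000, although the number who meet these three conditions is not given.

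**Consequences under each reading**, taking y = 80% for illustration and counting at the scan.

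- *Forty approached, then stop.* Scans 40 × 0.80 = 32; feasibility 32/40 = 80%.
- *Approach until 40.* Approaches 40 / 0.80 = 50; feasibility 40/50 = 80%.

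Both readings estimate the same quantity. Stopping at the 40th success calls, strictly, for (40 − 1)/(50 − 1) = 39/49 = 79.6% in place of 80.0%, a trivial difference. If the ceiling is counted at enrolment and, say, 95% of those enrolled are scanned, scans are 40 × 0.95 = 38, still within every stated limit.

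**Counting screen failures.** What is discarded is data collected at the screening visit. Consents and participant files are kept, so the numbers consented and found ineligible can be recovered. Refusals at re-contact come before that visit and are not affected.

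**The case for a change.** The strongest case for a change is that the three unqualified figures of 40 do not fit together as written. Reading the Overview as approaching people until 40 are enrolled adds words that it does not contain. Nor does that reading guarantee 40 scans: people who cannot be scanned are withdrawn from the study, which suggests that they were already in it, and if they use up places under the ceiling the scan count falls below 40. In a study whose first aim is recruitment feasibility, the number approached deserves a clear statement, and a clarifying sentence would cost little.

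Some of this stands. The Overview sentence is loose, 40 serves for three different stages, and the scan count may well end below 40. It does not follow that a result is at risk. The Protocol defines no feasibility measure that a wrong denominator could spoil, and how approaches and screen failures are logged and tabulated is commonly left to an analysis plan or recruitment procedures, neither of which is shown. Some doubt about research use of the files of ineligible people may remain, but it does not prevent counting them.

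The more ambitious remedy, making 40 the number of completed scans, has a cost. The tracer is injected up to 90 minutes before imaging, so a person injected but not successfully scanned would not count, and more than 40 people could receive an unapproved tracer.

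**Conclusion.** This is an ambiguity of wording, not an arithmetic error, and the plan can stand. The shortfall figures (20 to 38 scans from 40 contacts at yields of 50% to 95%, and a 13% chance of a full 40 at 95%) are correct as arithmetic. They test a commitment that the Protocol does not make, and every yield in them is assumed.

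Under either reading enrolment stays within the ceiling of 40, feasibility is the number scanned over the number approached, and Aim 2 uses the scans obtained. With no power or precision target stated, no declared property of the study changes. A team running this pilot would ordinarily keep a record of those approached, consented, eligible and scanned.

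The conclusion rests on two assumptions: that approaches are in fact logged, and that the Overview figure is not meant as a hard limit on contacts. If it were a limit, the feasibility result would still be valid as x out of 40, and the cost would be fewer scans for Aim 2.
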